3. LRBC

- i) Locally recurrent breast cancer with previous radiotherapy treatment (re-irradiation)

- **Primary objective:**

1. To assess the real-world implementation of superficial hyperthermia [using CE marked water-filtered infrared A (wIRA) machine] in addition to palliative SOC radiotherapy

- **Secondary objectives:**

1. To assess the best objective response rate (ORR) of the lesions treated with the combination of superficial hyperthermia (wIRA) and palliative radiotherapy
2. To determine the tolerability and safety profile of the combination treatment of superficial hyperthermia (wIRA) and palliative radiotherapy
3. To evaluate the median progression-free survival (PFS) and overall survival (OS) of patients
4. To assess the median duration of objective response and locoregional control rates at 6 and 12 months
5. To assess patient-reported outcome measures (PROMs) and quality of life (QoL) of patients using the European Organization for Research and Treatment of Cancer (EORTC) Quality of Life Core Questionnaire (QLQ-C30) and head and neck module (QLQ-H&N35)
6. To assess the differences in the efficacy between the lesion(s) treated with radiotherapy with hyperthermia with the lesion(s) treated with radiotherapy alone in those patients with at least 1 additional lesion that is not suitable for treatment with hyperthermia
7. To compare clinical outcome of patients treated with combination of superficial hyperthermia and radiotherapy who may or may not undergo subsequent immunotherapy with the retrospective data of historical cohorts

- **Exploratory objectives/translational research:**

Collection of samples such as archival tumour sample, fresh tumour biopsy/resected sample when available, blood (PBMC), and saliva, for translational research (see below).

- **Table 1: Objectives and endpoints**

	Objectives	Endpoints
--	-------------------	------------------

Primary	To assess the real-world implementation of superficial hyperthermia using CE marked water-filtered infrared A (wIRA) in addition to palliative SOC radiotherapy as part of their standard of care (SOC)	
1. Quantitative: the total number and types of cancer patients successfully treated with the combination of superficial hyperthermia and palliative radiotherapy.
 
2. Descriptive: to evaluate the real-world implementation by the NASSS (non-adoption, abandonment, and challenges to scale-up, spread, and sustainability) framework using NASSS-CAT (complexity assessment tool) ⁵

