Secondary	
1. To assess the best objective response rate (ORR) of the lesion(s) treated with (1) combination of superficial hyperthermia with palliative radiotherapy; (2) radiotherapy alone
 
2. To determine the tolerability and safety profile of superficial hyperthermia in patients receiving SOC palliative radiotherapy
 
3. To evaluate the median local and global progression-free survival (PFS) and median overall survival (OS) of patients at 12 months after the last patient is recruited
 
Local: refer to the lesions treated by radiotherapy +/- superficial hyperthermia.
 
Global: local and distant (non-treated lesions)
 
4. To assess the median duration of objective response and locoregional control rates of the treated lesion(s) at 6 and 12 months
	
1. Best ORR: Defined as the proportion of patients achieving either a Complete Response (CR) or a Partial Response (PR).
 
Complete Response (CR): Disappearance of all target lesions.
 
Partial Response (PR): ≥ 30% decrease in the sum of diameters of target lesions, taking as reference the baseline sum diameters.
 
2. Local adverse events (AEs) and adverse reactions (ARs) will be assessed by Common Terminology Criteria for Adverse Events (CTCAE) version 5.0.
 
3. PFS: Defined as the time from baseline to the first documented progressive disease (PD) or death from any cause, whichever occurs first.
 
PD: At least a 20% increase in the sum of diameters of target lesions or development of new lesions, with the date of progression recorded by a clinician in the patient's hospital records.
 
OS: The time from the start of treatment to death from any cause.
 
Patients not experiencing an event (progression or death) will be censored at the time of the final analysis at the date last known to be alive and progression-free.
 
4. Duration of Objective Response: Defined as the time from the first documented Complete Response (CR) or Partial Response (PR) to disease progression or metastasis.

		Locoregional Control Rate: The proportion of patients whose primary tumour site remains free from progression.

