	5. To assess patient-reported outcomes measures (PROMs)	
5. PROMs assessment using the European Organization for Research and Treatment of Cancer (EORTC) Quality of Life Core Questionnaire (QLQ-C30), European Organisation for Research and Treatment of Cancer Quality of Life Questionnaire Head and Neck Module (QLQ-H&N43) (for HNSCC cohort)
 
PROMs will be collected at baseline, during treatment (after the 3rd fraction of radiotherapy), 6 weeks post-treatment, 12-weeks post-treatment.

	6. To assess the differences in the efficacy between the lesion(s) treated with radiotherapy with hyperthermia with the lesion(s) treated with radiotherapy alone in those patients with at least 1 additional lesion that is not suitable for treatment with hyperthermia	6. Percentage of best ORR, duration of response and disease control rates at 6 and 12 months in the lesion(s) treated with hyperthermia and radiotherapy versus lesion(s) treated with radiotherapy alone.
	7. To compare clinical outcome of patients treated with superficial hyperthermia in addition to SOC radiotherapy with historical control	7. Retrospectively collect data for historical cohort of similar cancer patients treated with SOC radiotherapy alone

⁵Descriptive primary endpoint: evaluation of the real-world implementation by the NASSS-CAT

Introduction of the new technology into the NHS can be very complex and the process of which cannot be easily captured by the traditional clinical trial endpoints. To this end, the non-adoption, abandonment, scale-up, spread, and sustainability (NASSS) framework allows the description of the complexity in real-world implementation of new technology consisting of six domains including (a) the condition or illness, (b) the technology, (c) the value proposition, (d) the adopter system, (e) the health care organization(s), and (f) the wider system (especially regulatory, legal, and policy issues). The seventh domain is cross-cutting, considering how all these domains interact and emerge over time (27). Extending the NASSS framework and building on a complexity assessment tool (CAT), four NASSS-

CAT tools were previously developed to apply the complexity principles to evaluate the introduction of technology in healthcare setting (28). These includes NASSS-CAT SHORT, NASSS-CAT LONG, NASSS-CAT PROJECT and NASSS-CAT INTERVIEW (see appendix). We will use these tools to evaluate the descriptive part of the primary endpoint of this study.

7. Study design & Flowchart

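### PFS and OS start at different dates, and duration of response leaves out death while counting distant metastasis where it serves the lesion comparison of objective 6

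*Protocol*

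**What the plan says.** The definitions stand in the Protocol's Synopsis and again in Table 1 (section 6).

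- Endpoint 3 gives two time origins in one cell: "PFS: Defined as the time from baseline to the first documented progressive disease (PD) or death from any cause, whichever occurs first", then "OS: The time from the start of treatment to death from any cause".
- Endpoint 3 also contains the progression rule, "PD: At least a 20% increase in the sum of diameters of target lesions or development of new lesions", and a local category, "Local: refer to the lesions treated by radiotherapy +/- superficial hyperthermia". The only censoring rule sits here.
- Endpoint 4 describes duration of response as "Defined as the time from the first documented Complete Response (CR) or Partial Response (PR) to disease progression or metastasis".
- Endpoint 6 compares heated with unheated lesions on "Percentage of best ORR, duration of response and disease control rates at 6 and 12 months in the lesion(s) treated with hyperthermia and radiotherapy" and gives no definition of its own.
- Objective 7 compares clinical outcome with a historical cohort given radiotherapy alone.

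The endpoint text does not define baseline. Section 7 (Study design) equates it with the time of consent for blood sampling and lists the sample before the first treatment separately. The schedule of events marks consent at Baseline (Visit 1), with Pre-HT as Visit 2. Section 8 (Collection of biological samples) again lists the two as separate points. The remaining use, in the partial-response rule, is "taking as reference the baseline sum diameters", also a pre-treatment reference. Nothing limits the interval to treatment. Section 9 (Method of recruitment) only asks that treatment start in line with usual care.

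**The concern.** PFS and OS are reported for the same patients and are meant to nest, because every death is also a PFS event. With one origin, PFS cannot exceed OS. With two, it can. A patient who consents but never starts treatment has a PFS time but no OS start. The PFS origin also has no counterpart in a cohort collected retrospectively.

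Duration of response has two problems. First, PFS counts death a few lines earlier but duration of response does not, so a palliative patient who dies in response has no stated end date. Second, endpoint 4 supplies the only definition of the term, and objective 6 uses the term to compare lesions within patients. A distant metastasis then ends response in the heated and the unheated lesions on the same day, whatever happened in either. Deleting metastasis alone would not cure this, because the progression rule already counts new lesions.

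**Working it through.** The Protocol gives no figure that depends on these definitions and no power calculation (section 14), so there is nothing to reproduce. Gaps, death shares and event rates below are assumptions.

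**1. Two origins.** For a death without progression, PFS − OS = (death − consent) − (death − treatment start) = treatment start − consent = g. In months, g = weeks × 7 / 30.4375:

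- 1 week: 0.23
- 2 weeks: 0.46
- 4 weeks: 0.92

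For patients who progress first, PFS also contains g and OS does not, but PFS need not exceed OS.

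**2. Deaths in response.** Let p and q be constant hazards of progression and of death in response, and d = q/(p + q) the share of end events that are deaths.

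- Median with deaths censored: ln 2 / p.
- Median with deaths counted: ln 2 / (p + q).
- Ratio: (p + q)/p = 1/(1 − d).

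For d = 10%, 20% and 30% the ratio is 1.11, 1.25 and 1.43, an overstatement of 11%, 25% and 43%. Simulated Kaplan-Meier medians (300,000 patients) gave 1.114, 1.253 and 1.421. With Weibull hazards of common shape k the ratio is (1/(1 − d))^(1/k). For d = 10% to 30% that is 7% to 27% at k = 1.5 and 16% to 66% at k = 0.7.

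**3. Number of patients.** Three cohorts of 15 to 20 (section 8) make 45 to 60 patients. Section 5 quotes an overall clinical response of 54.9% with thermoradiotherapy. If that rate applied, 45 × 0.549 = 24.7 and 60 × 0.549 = 32.9 patients would respond. If all of them reached an end event, 10% of 24.7 is 2.5 and 30% of 32.9 is 9.9. So at most about 2 to 10 patients would have no defined end date.

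**4. Shared end date in objective 6.** Let c be the progression hazard of an unheated lesion, r × c that of a heated lesion, and m the hazard of a new distant lesion that ends response in both. The observed hazard ratio is (r × c + m)/(c + m). Assume a median of 6 months for the unheated lesion and r = 0.50. With a median time to distant disease of 12 months, the ratio is (0.5/6 + 1/12)/(1/6 + 1/12) = 0.167/0.25 = 0.67. With 6 and 24 months it is 0.75 and 0.60. The shared date pulls a real local difference towards none. The loss of precision cannot be sized, because the Protocol does not say how many patients will have a radiotherapy-only lesion.

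**The case against.** **Baseline may not mean consent.** The equation with consent is made for blood sampling, and the pre-treatment sample may be skipped when baseline blood exists. Consent is therefore the best-supported reading, not a stated rule for PFS. But every use of the word points to a time before treatment, and OS starts at treatment. The mismatch stands, and only its length is open.

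**Historical comparison.** A reader might infer that objective 7 is biased in favour of hyperthermia. The Protocol does not support that as a finding. It would require that PFS is among the outcomes compared, that controls are timed from radiotherapy, and that patients who progress or die before treatment are left out. None of these is stated. The size is also uninformative: between d × g and g, so 0.1 × 0.23 = 0.02 up to 0.92 months under the assumptions above. What stands is that the PFS origin cannot be dated in that cohort. No OS bias follows.

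**Lesion level.** Endpoint 6 does not cite endpoint 4, so the link is an inference. A natural reading of response in given lesions would ignore distant disease. But no other definition is offered. For objective 4 a patient-level reading is possible, since the list in section 6 reads "To assess the median duration of objective response and locoregional control rates at 6 and 12 months" without the restriction to treated lesions found in Table 1. The lesion-level point therefore rests on objective 6.

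**Death as a lesion event.** Counting death as an end event for lesions would recreate the shared date complained of. This objection is right, and the fix allows for it.

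**Importance.** These are secondary endpoints of an implementation study. The continuation criteria in section 9 (End of Study Definition) are recruitment, implementability and funding. This also stands.

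**Conclusion.** The concern holds in a limited form. Followed as written, the definitions let PFS exceed OS by the consent-to-treatment gap in a death without progression, leave death in response without event status, and offer the lesion comparison only a patient-level end point. These are rules the Protocol states, not detail left for later.

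The sizes are illustrative: 0.23 to 0.92 months for a 1 to 4 week gap, and an 11% to 43% longer median duration of response if deaths are censored and make up 10% to 30% of end events under constant hazards. The Protocol does not say that deaths would be censored; that is the usual default when death is not an event. A reader might go further and conclude that PFS and OS are unusable together. That is too strong, because the reversal occurs only in deaths without progression and only by the gap. The primary endpoint and the continuation criteria are untouched. It should be fixed because the fix is cheap, not because it threatens the study's main conclusion.

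**What to change.** In Table 1 and the Synopsis:

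- Start both PFS and OS at the first study treatment session, and at the first radiotherapy fraction for historical controls. Report consented but untreated patients as a count.
- In patient-level duration of response, count death from any cause as an event.
- For objective 6, and for objective 4 where it concerns treated lesions, end response at progression of those lesions only, in line with the existing Local category. New lesions elsewhere then do not count. Treat death as a competing event and report the number of deaths in response.

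The change uses treatment and death dates that a clinical record would hold and alters no treatment, visit or sample. It needs a wording amendment with Sponsor and REC review (section 15). The downside is that median PFS and patient-level duration of response will read slightly shorter.

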Primary	To assess the real-world implementation of superficial hyperthermia using CE marked water-filtered infrared A (wIRA) in addition to palliative SOC radiotherapy	
 1. Quantitative: the total number and types of cancer patients successfully treated with the combination of superficial hyperthermia and palliative radiotherapy. 2. Descriptive: to evaluate the real-world implementation by the NASSS (non-adoption, abandonment, scale-up, spread, and sustainability) framework using NASSS-CAT (complexity assessment tool)
Secondary	1. To assess the best objective response rate (ORR) of the lesion(s) treated with combination of superficial hyperthermia with palliative radiotherapy	
 1. Best ORR: Defined as the proportion of patients achieving either a Complete Response (CR) or a Partial Response (PR). Complete Response (CR): Disappearance of all target lesions.

		Partial Response (PR): $\geq 30\%$ decrease in the sum of diameters of target lesions, taking as reference the baseline sum diameters.
	2. To determine the tolerability and safety profile of superficial hyperthermia in patients receiving SOC palliative radiotherapy	2. Local serious adverse events (SAEs) will be assessed by Common Terminology Criteria for Adverse Events (CTCAE) version 5.0.
	3. To evaluate the median local and global progression-free survival (PFS) and median overall survival (OS) of patients at 12 months after the last patient is recruited	
3. Patients not experiencing an event (progression or death) will be censored at the time of the final analysis at the date last known to be alive and progression-free.
 
Local: refer to the lesions treated by radiotherapy +/- superficial hyperthermia.
 
Global: local and distant (non-treated lesions)
 
PFS: Defined as the time from baseline to the first documented progressive disease (PD) or death from any cause, whichever occurs first.
 
Progressive disease (PD): At least a 20% increase in the sum of diameters of target lesions or development of new lesions, with the date of progression recorded by a clinician in the patient's hospital records.
 
OS: The time from the start of treatment to death from any cause.

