The patient recruitment for the prospective study will initially be 24 months from the commencement of the study at coordinating site, Guy's and St. Thomas' NHS Foundation trust. Thereafter, the patients will be followed up for their long-term treatment outcome and survival as per normal standard of care. We will continue to obtain relevant information on patients' treatment and survival outcome from patients' medical records. The end of the study definition is 12 months from the last participant recruited into the study. We will assess whether the endpoints and outcomes are met at the end of the study, particularly the real-world implementation of superficial hyperthermia (using CE marked water-filtered infrared A (wIRA) machine) in addition to palliative radiotherapy and whether we are able to recruit the target number of patients.

We will submit the protocol for a major amendment towards the end of the study if the study is to continue for up to an additional 3 years of recruitment, providing further funding is obtained. Otherwise, we will analyse all data and produce the final study report at the end of third year.

The criteria for progression beyond the two-year recruitment period are set as below:

1. The study recruits well and reaches the target number of patients (up to 60 patients)
2. The study showed that superficial hyperthermia with wIRA could be implemented in the real-world setting and used in combination with palliative radiotherapy in cancer patients
3. Further funding is obtained to continue beyond the two-year recruitment period

10. Laboratories

Collected patients' samples from Guy's Hospital as part of translational research will be transferred to [name] laboratory at Kings College London for further processing. The samples will be pseudo-anonymised with sample IDs which can be linked to patients. The sample processing will be done by the research assistant appointed for the study and/or [name] lab members and only those with KHP passport will have access to patients' confidential information. The samples will not be transferred or given to anyone without an MTA agreement. However, if there are any successfully generated organoids from any fresh samples, the anonymised organoids may be shared with collaborators. Based on the consent from patients, any other unused blood, saliva, oral swab, urine, and stool samples will be stored at Guy's and St Thomas' head and neck biobank beyond the ethics approval date of the project.

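### The only censoring sentence for secondary endpoint 3 uses the PFS event and the PFS date but is not limited to PFS, so it does not fit OS

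*Protocol*

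**What the plan says.** The objective is to estimate median local and global PFS and "median overall survival (OS) of patients at 12 months after the last patient is recruited". The definitions are in section 6, Table 1, secondary endpoint 3, and again in the section 4 synopsis.

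- PFS: "Defined as the time from baseline to the first documented progressive disease (PD) or death from any cause, whichever occurs first".
- OS: "OS: The time from the start of treatment to death from any cause".
- Censoring: "Patients not experiencing an event (progression or death) will be censored". They are to be "censored at the time of the final analysis at the date last known to be alive and progression-free", so the date is the last one on which the patient was known to be both alive and free of progression.

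The position of the censoring sentence differs. In Table 1 it comes directly after the OS definition. In the synopsis it opens the endpoint, ahead of both definitions: "Patients not experiencing an event (progression or death) will be censored at the time of the final analysis". Neither place restricts it to PFS, and no separate OS censoring rule appears elsewhere in the protocol.

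On follow-up, section 9 (End of Study Definition) states: "The patient recruitment for the prospective study will initially be 24 months". The study ends 12 months after the last participant is recruited, and survival continues to be taken from medical records during that time.

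**The concern.** OS has one event, death. Progression is neither an OS event nor a reason to stop counting survival time. A censoring sentence that lists progression as an event and requires freedom from progression at the censoring date therefore fits PFS and does not fit OS.

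The patients affected are those alive after progression. There may be a fair number of them, because section 7 expects many HNSCC and cSCC patients to be suitable for immunotherapy after radiotherapy. If their survival time after progression is discarded while deaths after progression still count, the OS curve is pulled down. Secondary objective 7 compares clinical outcome with a historical cohort. If OS is among those outcomes and the historical patients are censored at last contact, the understatement would count against the combination. Section 14 also says that the data will be used to size later work.

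**Working it through.** **Step 1: the readings.** The protocol gives no survival, event or power figure for this endpoint, so there is no planned number to reproduce. For a patient alive after progression, the sentence applied to OS allows three readings:

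| Reading | Effect on OS |
|---|---|
| A. Censor at the last progression-free date | Observed survival time is lost; OS understated |
| B. Progression is the event, as the parenthesis lists it | OS becomes PFS; OS understated |
| C. The patient has had a listed event, so is not covered | No OS rule for this group |

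A fourth possibility, censoring everyone at progression and dropping later deaths, would overstate OS. It contradicts the definition of OS as death from any cause and is set aside.

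**Step 2: mechanism of reading A, by hand.** Ten invented patients: deaths at 5, 8, 10, 12 and 14 months; five alive at 18 months whose last progression-free dates are 3, 4, 4, 6 and 9 months.

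- Survivors censored at 18 months: all ten stay at risk until the deaths. S(12) = 6/10 = 0.60, and the median is 14 months.
- Survivors censored at the last progression-free date: the risk sets at the first four deaths are 7, 5, 3 and 2. S(10) = 6/7 × 4/5 × 2/3 = 0.457, so the median is 10 months. S(12) = 0.457 × 1/2 = 0.229.

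**Step 3: size under reading A.** Follow-up is taken as uniform over 12 to 36 months (24 months of recruitment plus 12). The medians are assumptions. Death has constant hazard d = ln 2 / median OS. The PFS hazard is q = ln 2 / median PFS, so progression has hazard q − d. The share progressed and alive at cut-off is the average of exp(−df) − exp(−qf) over f from 12 to 36. For OS 18 and PFS 6, d = 0.0385 and q = 0.1155, so the share is (0.630 − 0.250)/(24 × 0.0385) − (0.250 − 0.0156)/(24 × 0.1155) = 0.411 − 0.085 = 0.33. Kaplan-Meier on 400,000 simulated patients per row, with survivors censored at progression, gives:

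| Assumed median OS / PFS (months) | Progressed and alive | Median OS under reading A | 12-month OS, true to reading A | 24-month OS, true to reading A |
|---|---|---|---|---|
| 8 / 4 | 12% | 7.5 | 35% to 31% | 12% to 5% |
| 12 / 6 | 19% | 10.7 | 50% to 45% | 25% to 14% |
| 18 / 6 | 33% | 13.7 | 63% to 56% | 40% to 20% |

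The losses in the median are 0.5, 1.3 and 4.3 months.

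**Step 4: a different model.** Assumed here: 15% of PFS events are deaths without progression, assessments are 3-monthly, and survivors are censored at the last progression-free assessment.

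| Median PFS / median survival after progression (months) | Median OS, true to reading A | Loss |
|---|---|---|
| 4 / 6 | 10.6 to 9.8 | 0.9 (unrounded 10.63 − 9.77) |
| 6 / 9 | 16.0 to 13.5 | 2.5 |
| 9 / 12 | 22.7 to 18.1 | 4.6 |
| 6 / 18 | 23.4 to 15.8 | 7.6 |

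With near-continuous assessment the second row becomes 16.0 to 13.8, so the loss comes mainly from discarding time after progression and not from visit spacing.

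**Step 5: reading B.** OS equals PFS. In these scenarios the reported median would be the PFS median, 4 to 9 months.

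**The case against.** The strongest reply is that this is a PFS sentence in a shared table cell. It names the PFS event and uses the term progression-free, while OS has its own definition. Read literally, it covers only patients without progression, so a patient alive after progression falls outside it. For those it does cover, the last date alive and progression-free is close to the last date alive, and OS is little affected. Section 9 continues survival follow-up, and the schedule of events runs past progression, which points away from stopping OS there. On that view the protocol merely lacks an OS censoring rule, which a statistical analysis plan would normally supply.

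Much of this stands. The sentence was probably meant for PFS. A reader might infer that the protocol definitely cuts survivors off at progression and so will report OS too low. The text does not establish that, because reading A is one of three. A reader might also infer that the sentence sets two rival censoring dates. It does not: the reference to the final analysis reads naturally as the data cut-off, and the only patient-level date is the last known one.

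The reply does not remove the point. The protocol does more than stay silent: it states a rule over an endpoint that includes OS, in two places, and the rule does not fit OS.

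On consequence, OS is one of several secondary endpoints in an implementation study with no formal power calculation. Continuation depends on recruitment, implementation and funding, and objective 7 does not name OS. With 60 patients the simulated standard error of median OS is about 1.5, 2.3 and 3.8 months in the three scenarios of step 3, so the first two shifts are smaller than sampling error. The shift is nonetheless systematic and avoidable.

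**Conclusion.** The point holds as a defect of wording: one stated rule covers PFS and OS and is valid only for PFS. Two of the three ways to apply it to OS understate survival, and the third leaves patients alive after progression without a rule.

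Under reading A the median OS falls by about 0.5 to 4 months when median OS is 8 to 18 months and median PFS 4 to 6 months. The loss reaches 7.6 months where median survival after progression is 18 months. These survival times are assumptions; only the 12 to 36 months of follow-up comes from the protocol. The direction was the same in every scenario under both models. The bias is small if most patients die before cut-off and larger if many are alive after progression. Any bias in the historical comparison further requires that OS is compared and that the historical cohort is censored at the date last known alive.

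The correction should be made, but the point does not threaten the primary endpoint.

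**What to change.** In the section 4 synopsis and in section 6, Table 1, secondary endpoint 3:

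1. Limit the existing censoring sentence to local and global PFS.
2. Add a sentence for OS: patients not known to have died are censored at the date last known alive, whatever their progression status.
3. If OS is compared with the historical cohort under objective 7, state that the same OS rule applies there.

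The cost is a short wording change in two places. No new data are needed, since survival is already collected from medical records.
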